4.0 Inclusion and Exclusion Criteria Inclusion

Criteria:

1. Patients 18 years of age or older with histological documentation of metastatic colorectal cancer (mCRC).
2. ECOG performance status of 0-2.

3. Radiographical documentation of metastatic disease with imaging up to 6 weeks prior to enrollment.
4. Patients with mCRC must have been previously treated with irinotecan and/or oxaliplatin and/or VEGF/EGFR therapy or intolerant to these agents
5. Documentation of K-Ras mutational status
6. Adequate hematologic, renal and liver function (i.e. absolute neutrophil count $> 1000/\text{mm}^3$, platelets $> 75,000/\text{mm}^3$); creatinine < 2 times the upper limits of normal (ULN) total bilirubin $< 1.5 \text{ mg/dl}$, ALT and AST < 3 times above the ULN, ALT and AST can be < 5 times ULN if patients have hepatic involvement.
7. Able to provide written informed consent.
8. Patients with the potential for pregnancy or impregnating their partner must agree to follow acceptable birth control methods to avoid conception. Women of childbearing potential must have a negative pregnancy test within 72 hours prior to receiving the investigational product.
9. Tumor blocks available from previous surgery/biopsy, or if not available, patients willing to have biopsy.

Exclusion Criteria:

1. Patients receiving prior therapy with RGF, VOR, and/or HCQ.
2. Patients with uncontrolled brain metastases. Patients with brain metastases must be asymptomatic and off corticosteroids for at least one week.
3. Due to risk of disease exacerbation, patients with porphyria are not eligible.
4. Due to risk of disease exacerbation, patients with psoriasis are ineligible unless the disease is well controlled, and they are under the care of a specialist for the disorder who agrees to monitor the patient for exacerbations.
5. Patients with previously documented macular degeneration or untreated diabetic retinopathy (stable retinopathy is allowed).
6. Patients who have had chemotherapy or radiotherapy within 2 weeks (6 weeks for nitrosoureas or mitomycin C) prior to entering the study. For investigational targeted therapies, patients will need to clear for 5 half-lives (not applicable to standard of care therapies).
7. Patients may not be receiving any other investigational agents.
8. Patients should not have taken valproic acid or another histone deacetylase inhibitor for at least 2 weeks prior to enrollment.

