This will be a phase II randomized clinical trial of patients with histologic documentation of metastatic colorectal cancer, who have received local and currently approved standard therapies, excluding RGF. Patients will be randomized 1:1 to RGF or VOR/HCQ (see schema below) and stratified by KRAS status (wild-type or mutated). We will give VOR 400 mg PO daily and HCQ 600 mg PO daily in 4-week cycles. Patients will require imaging up to 6 weeks prior to enrollment and will be assessed for measureable evidence of mCRC. Crossover to the other arm will be allowed, but OPTIONAL, and will be determined by the treating physician for the patient's best interest.

5.1 Sample size:

Historically, the mPFS for previously treated mCRC patients treated with RGF is 1.9 mos. We predict VOR/HCQ will improve mPFS to 3.8 months. We expect 5% lost to follow-up. Assuming a 36-month accrual period with 1 year for follow up, 36 subjects per group are necessary to obtain 80% power. With 5% lost to follow-up the sample size required per group is 38 ($=36/0.95$), therefore, the total required sample size is 76 subjects. As a result, the target accrual rate is 2-4 patients/month to achieve a target accrual at 36 months with an additional 12month follow-up.

5.2 Study Schema:

*** Crossover to the other arm will be allowed, but OPTIONAL, and will be determined by the treating physician for the patient's best interest.

Randomization:

Randomization list will be sent to pharmacy. Once the patient is registered onto the study, the pharmacist will assign the patient to one of the treatment arms. The patient should start the treatment within 14 days of randomization.

Upon randomization, regorafenib prescription will be sent to specialty pharmacy. If the patient receives the medication in <14 days, then the patient can start at home. The start date will be C1D1. If the patient receives ≥ 14 days, then the patient will need a C1D1 clinical visit and labs: CBC, CMP, CEA and biomarkers.

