10.0 Statistical Section

Analytic plan for primary objective:

mPFS-1: Historically, the mPFS for previously treated mCRC patients treated with RGF is 1.9 mos. We predict VOR/HCQ will improve mPFS to 3.8 months. We expect 5% lost to followup. Assuming a 36-month accrual period with 1 year for follow up, 36 subjects per group are necessary to obtain 80% power. With 5% lost to follow-up the sample size required per group is 38 ($=36/0.95$), therefore, the total required sample size is 76 subjects. As a result, the target accrual rate is 3-4 patients/month to achieve a target accrual at 36 months with an additional 12month follow-up.

Treatments will be contrasted with regard to PFS-1 with a proportional hazards model with adjustment for age, sex, race, and the baseline tumor K-RAS status (mutated, wild type); the adjusted hazard ratio, its 95% confidence interval, and the p-value for testing the null hypothesis that the log hazard ratio is zero will be presented. Survival curves will be illustrated with Kaplan-Meier plots. Interactions between treatment and baseline covariates will be explored.

If a patient does not complete Cycle 1 and is off study, then this patient will not be evaluable for efficacy but will be evaluable for toxicity.

Interim analysis: The O'Brien-Fleming procedure will be used to conduct an interim analyses for efficacy when 50% of the patients complete the study. A statistical basis for stopping the study at the first look will be achieved if the test statistic indicates benefit in the VOR/HCQ Arm and exceeds 2.96259, corresponding to a significance level of 0.003. If the test statistic does not exceed 2.96259 at the first look then the trial will proceed to the final analysis. A treatment effect will be declared significant and beneficial at the final analysis if the test statistic indicates benefit and exceeds 1.96857, corresponding to a significance level of 0.047. If a treatment effect is not declared at the interim analysis, a statistical basis for stopping the study for futility will be attained if the conditional power is less than or equal to 20%.

Analytic plan for secondary objectives:

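### The primary PFS-1 Cox model omits baseline ECOG, which is already collected; adding it would cost at most about one point of power and would gain several if ECOG proves prognostic

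*Combined protocol and SAP*

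**What the plan says.** The primary analysis in Section 10.0 is a "proportional hazards model with adjustment for age, sex, race, and the baseline tumor K-RAS status", reported as an adjusted hazard ratio with its confidence interval and p-value. No reason is given for the choice of covariates.

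Eligibility in Section 4.0 requires "ECOG performance status of 0-2". The study calendar in Section 6.0 (Table 4 and the baseline checklist) records ECOG at baseline, so every eligible patient should have a value. Section 5.0 randomises 1:1 with KRAS status as the only stratification factor. ECOG appears in none of the models in Section 10.0.

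The sample size rests on a historical control figure ("the mPFS for previously treated mCRC patients treated with RGF is 1.9 mos"), a predicted doubling of that median in the experimental arm, and this statement of design and power: "Assuming a 36-month accrual period with 1 year for follow up, 36 subjects per group are necessary to obtain 80% power". An allowance of 5% for loss then raises the group size from 36 to 38. No part of this refers to covariate adjustment.

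**The concern.** If a baseline variable is prognostic and is left out of a Cox model, the treatment hazard ratio is pulled towards 1 and the test loses power. The trial admits three performance grades and has 76 patients. ECOG is neither stratified nor adjusted for, so a chance difference between arms can also move the one estimate that the trial will produce. The documents make some link with PFS-1 plausible: the endpoint also ends when a patient comes off study for any reason (Section 5.7), and treatment may stop for toxicity, withdrawal or physician decision (Section 5.3.1). They do not say how strong the link is.

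The value is already collected, so the question is whether one further model term, fixed in advance, buys enough to justify its cost.

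**Working it through.** **1. The plan's own figure.** Inputs from Section 10.0: medians 1.9 and 3.8 months, 80% power, 36 months of accrual, 12 months of follow-up, 5% loss. The sample size text does not state alpha. Two-sided 0.05 is assumed, which fits the interim rule ("exceeds 2.96259, corresponding to a significance level of 0.003"), since 2.96259 is two-sided p = 0.00305.

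- Hazard ratio under exponential PFS: 1.9/3.8 = 0.50.
- Freedman events: (1.960 + 0.842)² × [(1 + 0.5)/(1 − 0.5)]² = 7.85 × 9 = 70.6, so 71.
- Event probability, uniform accrual: 1 − (e^(−12λ) − e^(−48λ))/(36λ), with λ = ln 2/median. This gives 0.999 for RGF and 0.983 for VOR/HCQ, mean 0.991.
- Per group: 71/0.991/2 = 35.8, so 36. After loss: 36/0.95 = 37.9, so 38.

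Both figures match the plan. Schoenfeld's formula gives 66 events and 34 per group. One-sided 0.05 gives 27 to 29 per group and does not match. No covariate enters any of these formulas.

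**2. Effect of adding ECOG.** The documents supply no ECOG effect and no ECOG distribution, so both are assumptions shown over a range: hazard ratio per grade 1.0 to 2.5, and ECOG 0/1/2 mixes of 50/50/0, 40/50/10 and 30/50/20 percent. The simulation used:

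- 10,000 trials per scenario, 36 per arm;
- treatment hazard ratio 0.50 within grade, with the overall control median scaled to 1.9 months;
- age, sex, race and K-RAS in both models, with no prognostic effect;
- ECOG as a linear term in the second model only;
- a Wald test at two-sided 0.05, with no interim look.

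Ranges are over the three mixes.

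| Assumed HR per grade | Power without ECOG | Power with ECOG | Change, points |
|---|---|---|---|
| 1.0 | 0.80 | 0.79 | −0.3 to −0.5 |
| 1.25 | 0.77–0.79 | 0.78–0.79 | 0 to +1 |
| 1.5 | 0.75–0.77 | 0.79 | +2 to +4 |
| 2.0 | 0.67–0.73 | 0.78–0.79 | +6 to +11 |
| 2.5 | 0.61–0.69 | 0.77–0.79 | +10 to +16 |

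Monte Carlo error is about 0.4 points on each power. The mechanism shows in the estimates: at 2.0 per grade the median estimated hazard ratio is 0.51 to 0.53 without ECOG and 0.48 with it.

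A separate run with 38 per arm and three other covariates gave, without and with ECOG, 80 and 79% at 1.0, 78 and 79% at 1.3, 74 and 78% at 1.6, and 70 and 80% at 2.0. Two further runs with 38 per arm gave gains of 5 and 6 points at 1.6, so the gain there may be slightly above 4.

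**3. Type I error.** With the 40/50/10 mix and hazard ratios per grade of 1.0, 1.5 and 2.0, two-sided error was 0.064 to 0.068 without ECOG and 0.063 to 0.072 with it. Both models sit somewhat above 0.05, and adding ECOG makes no material difference.

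**4. Chance imbalance.** With an assumed 35/50/15 mix the variance of ECOG is 1.10 − 0.80² = 0.46. The standard deviation of the between-arm difference in mean ECOG is then √(2 × 0.46/38) = 0.156. To first order, a one-SD imbalance at 1.5 per grade shifts the unadjusted log hazard ratio by 0.156 × ln 1.5 = 0.063, or about 6%.

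**The case against.** The strongest reply is that nothing in the plan is wrong. The covariates are prespecified and include the one stratification factor, the sample size reproduces without any covariate, and randomisation protects the test whether or not ECOG is in the model. The documents give no ECOG effect, and with a weak effect the gain is nil. All of this stands. It makes the point a conditional gain in efficiency, with no fault in validity.

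A second reply is that fixing 0.50 within grade favours adjustment, because the plan's 0.50 comes from overall medians. This does not hold. If PFS is exponential within each grade and treatment halves every hazard, then S_VOR(t) = Σ p_k exp(−λ_k t/2) = S_RGF(t/2), so the overall median doubles exactly from 1.9 to 3.8. A run with those overall medians (3,000 trials per scenario, 38 per arm, mix 35/50/15, cutoff 1.96857) gave power without and with ECOG of 78 and 81% at 1.5 per grade and 70 and 81% at 2.0. The reply would apply only if 0.50 were taken as the unadjusted Cox hazard ratio itself.

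A reader might go further and infer any of the following. The documents support none of them.

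- *The trial is underpowered or N = 76 is wrong.* The planned figures are correct for the calculation made, and any shortfall depends on an ECOG effect that the documents do not give.
- *Chance imbalance in ECOG biases the test.* It affects precision and the single realised estimate; error rates are materially the same with and without ECOG.
- *Race should be collapsed or removed to make room.* Section 10.0 does not say how race is coded, the mix in Section 9.0 is only a projection, and no calculation here measures a gain from changing it.
- *ECOG belongs in the secondary models too.* Only PFS-1 was examined. The logistic response model already has a fallback for small cell counts, and a further term could make that failure more likely.

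**Conclusion.** The point holds as a conditional improvement. The primary model leaves out a baseline variable that is required for entry, recorded for everyone and not balanced by stratification. Adding it costs about 0.5 to 1 point of power if ECOG has no effect and changes nothing material at about 1.25 to 1.3 per grade. It gains about 2 to 4 points at 1.5 to 1.6 and 6 to 11 points at 2.0. These sizes rest on assumed ECOG mixes, a log-linear ECOG effect, exponential PFS within grade and a within-grade treatment hazard ratio of 0.50. The case for the change is the asymmetry between a small, bounded cost and a useful gain over a moderate range.

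**What to change.** In Section 10.0, add baseline ECOG to the covariate list of the primary PFS-1 proportional hazards model and state its coding, for example a single linear term for 0/1/2. Make the change before data are analysed, including for the interim look; a covariate added after the comparison has been seen would be open to challenge. It is one line of text. It needs no new data and no change to the sample size, and it uses one model parameter.

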In addition, HDAC has been well-recognized as potential targets for the treatment of numerous aging-related disorders (9) such as cancer (10). Therefore, we plan to evaluate the potential role of biomarkers of aging with the combination of HCQ plus VOR.

These findings support a phase II study VOR/HCQ versus standard therapy RGF in patients failing standard therapies.

We hypothesize that VOR/HCQ will have improved efficacy when compared to RGF in treatment-refractory mCRC patients. This hypothesis is based on the observations that:

1. In refractory mCRC patients, the role of continued VEGF inhibition in mCRC has not been established (4).
2. Only a modest improvement in survival was reported with the use of RGF, an oral multi-kinase inhibitor with predominantly angiogenic inhibition, for mCRC patients who have failed standard therapies (3).
3. Autophagy inhibition enhances vorinostat-induced apoptosis via ubiquitinated protein accumulation in CRC models pre-clinically (5).
4. Clinical activity based on treatment-refractory mCRC patients enrolled in phase I (6) and the ongoing single arm Phase II study of VOR with HCQ therapy suggests a median PFS of > 3 months.

Our overall objective is to answer these questions: will VOR/HCQ be more efficacious than RGF, will VOR/HCQ be safe, and can biomarkers be identified that will predict clinical efficacy of VOR/HCQ and RGF in refractory mCRC patients?

Primary Objective(s):

- To determine the clinical efficacy with progression-free survival (PFS-1) of the combination of VOR plus HCQ when compared to RGF in treatment-refractory mCRC.

Secondary Objective(s):

- To determine the overall survival in refractory mCRC patients receiving VOR plus HCQ when compared to RGF.
- To determine the progression-free survival (PFS-2) of the crossover treatment, which is optional.
- To evaluate the tumor response rate in refractory mCRC patients receiving VOR plus HCQ when compared to RGF.
- To further define the safety of the combination of VOR/HCQ when compared to RGF in treatment-refractory mCRC.
- To identify biomarkers of autophagy and anti-angiogenic inhibition that are associated with clinical efficacy of VOR/HCQ and RGF, respectively, in mCRC.

Primary Endpoint(s):

- PFS-1: measured from the start of the first treatment the patient is randomized to until the date the criteria for progression are met or the date the patient is taken off study for any reason, whichever is shorter.

[figure not shown]
Secondary Endpoint(s):

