- OS: measured from the start of treatment on trial until the death of the patient.
- mPFS-2: measured from the start of the crossover treatment (second regimen, which is optional) until the date the criteria for progression are met or the date the patient is taken off study for any reason, whichever is shorter.

- Response: measured as best response, complete response (CR) or partial response (PR), as defined by Response Evaluation Criteria in Solid Tumors (RECIST 1.1) Committee.
- Adverse events: grade 1-5 adverse events according to the National Cancer Institute Common Terminology Criteria for Adverse Events (NCI-CTCAE) v4.0; measured at baseline, each cycle, and at off study date.
- Biomarkers of efficacy of VOR/HCQ and RGF: evaluate biomarkers of autophagy and anti-angiogenic inhibition that are associated with clinical efficacy of VOR/HCQ and RGF, respectively, in mCRC.

Study Design:

This will be a randomized phase II clinical trial of patients with histologic documentation of metastatic colorectal cancer, who have received local and currently approved standard therapies, excluding RGF. We will give VOR 400 mg PO daily and HCQ 600 mg PO daily in 4-week cycles. Patients will require imaging up to 6 weeks prior to enrollment and will be assessed for measurable evidence of mCRC. This will be a randomized, controlled phase II clinical trial of patients with histological documentation of metastatic colorectal cancer, who have received locally and currently approved standard therapies, excluding RGF. Patients will be randomized 1:1 to RGF or VOR/HCQ (see schema below). Also, crossover is optional after first progression on the initial therapy, and based on physician discretion and in the best interest of the patient. If crossover is not done, then the patient will be off study and can go on to receive other treatments.

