- mPFS-1: Historically, the mPFS for previously treated mCRC patients treated with RGF is 1.9 mos. We predict VOR/HCQ will improve mPFS to 3.8 months. We expect 5% lost to follow-up. Assuming a 36-month accrual period with 1 year for follow up, 36 subjects per group are necessary to obtain 80% power. With 5% lost to follow-up the sample size required per group is 38 ($=36/0.95$), therefore, the total required sample size is 76 subjects. As a result, the target accrual rate is 2-4 patients/month to achieve a target accrual at 36 months with an additional 12-month follow-up.

Interim analysis: The O'Brien-Fleming procedure will be used to conduct an interim analyses for efficacy when 50% of the patients complete the study. A statistical basis for stopping the study at the first look will be achieved if the test statistic indicates benefit in the VOR/HCQ Arm and exceeds 2.96259, corresponding to a significance level of 0.003. If the test statistic does not exceed 2.96259 at the first look then the trial will proceed to the final analysis. A treatment effect will be declared significant and beneficial at the final analysis if the test statistic indicates benefit and exceeds 1.96857, corresponding to a significance level of 0.047. If a treatment effect is not declared at the interim analysis, a statistical basis for stopping the study for futility will be attained if the conditional power is less than or equal to 20%.

Analytic plan for secondary objectives:

- OS: The analyses of median OS will be performed in the intent-to-treat population. OS will be illustrated with Kaplan-Meier plots, the estimate of median OS with its 95% confidence interval.
- mPFS-2: The analyses of median PFS-2 will be performed in the crossover population (crossover is optional). mPFS-2 will be illustrated with Kaplan-Meier plots, the estimate of median PFS-2 with its 95% confidence interval. Treatment groups will be contrasted with regard to the response rate with a logistic regression model adjusted for age, sex, race and the baseline tumor K-RAS status (mutated, wild type); the odds ratio, its 95% confidence interval, and the p-value for testing the null hypothesis that the log odds ratio is zero will be presented. If the logistic model fails due to small cell counts then treatments will be contrasted with regard to response using Fisher's Exact Test.

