Hepatic: AST increased (58% to 65%; grade 3: 3% to 5%; grade 4: 1%), ALT increased (39% to 45%; grade 3: 4% to 5%; grade 4: 1%), hyperbilirubinemia (33% to 45%)

Neuromuscular & skeletal: Stiffness (14%)

Renal: Proteinuria (33% to 60%; grade 3: 3%)

Miscellaneous: Infection (31% to 32%; grade ≥ 3 : 5% to 9%) 1%
to 10%:

Cardiovascular: Myocardial ischemia and infarction (1%)

Gastrointestinal: Taste disturbance (8%), xerostomia (5%), gastroesophageal reflux (1%)

Neuromuscular & skeletal: Tremor (2%)

Respiratory: Dyspnea (2%)

<1% (Limited to important or life-threatening): Bradycardia, erythema multiforme, gastrointestinal fistula, hypertensive crisis, liver injury (severe), liver failure, reversible posterior encephalopathy syndrome (RPLS), skin cancer (keratoacanthoma, squamous cell carcinoma), Stevens-Johnson syndrome, toxic epidermal necrolysis

Pregnancy Category D:

Risk Summary Based on its mechanism of action, Regorafenib can cause fetal harm when administered to a pregnant woman. There are no adequate and well-controlled studies with Regorafenib in pregnant women. Regorafenib was embryo lethal and teratogenic in rats and rabbits at exposures lower than human exposures at the recommended dose, with increased incidences of cardiovascular, genitourinary, and skeletal malformations. If this drug is used during pregnancy or if the patient becomes pregnant while taking this drug, the patient should be apprised of the potential hazard to a fetus

5.7 Primary and Secondary Endpoints: Primary endpoint:

- PFS-1: measured from the start of the first treatment the patient is randomized to until the date the criteria for progression are met or the date the patient is taken off study for any reason, whichever is shorter.

Secondary endpoints:

- OS: measured from the start of treatment on trial until the death of the patient.

- mPFS-2: measured from the start of the crossover treatment (OPTIONAL, second regimen) until the date the criteria for progression are met or the date the patient is taken off study for any reason, whichever is shorter.
- Response: measured as best response, complete response (CR) or partial response (PR), as defined by Response Evaluation Criteria in Solid Tumors (RECIST 1.1) Committee.
- Adverse events: grade 1-5 adverse events according to the National Cancer Institute Common Terminology Criteria for Adverse Events (NCI-CTCAE) v4.0; measured at baseline, each cycle, and at off study date.

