7.0 Data Collection

Data will be entered into Case Report Forms (CRF), which are currently in paper form.

For each patient on study, the following will be documented:

- Lab values: CBC, CMP, CEA, PTT/INR (when collected)
- PFS-1: measured from the start of the first treatment the patient is randomized to until the date the criteria for progression are met or the date the patient is taken off study for any reason, whichever is shorter).
- OS: measured from the start of treatment on trial until the death of the patient (date of death)
- PFS-2: measured from the start of the crossover treatment (Optional, second regimen) until the date the criteria for progression are met or the date the patient is taken off study for any reason, whichever is shorter.
- Response: measured as best response at any given time: complete response (CR) or partial response (PR), as defined by Response Evaluation Criteria in Solid Tumors (RECIST 1.1) Committee (73). (See Appendix 13.1 for definitions of response).
- Adverse events: the number and grade 1-5 of all adverse events will be documented according to the National Cancer Institute Common Terminology Criteria for Adverse Events (NCI-CTCAE) v4.0; measured at baseline, each cycle, and at off study date.

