- Biomarkers of efficacy of VOR/HCQ and RGF: Biomarkers will be graphically displayed to demonstrate patterns across time and group and to identify the need for transformations and potential outliers. The significance of variation in biomarkers with treatment will be assessed with linear models with and without adjustment for age, sex, race and the baseline tumor KRAS status (mutated, wild type). The dependent variables will be log transformed (base 2) if necessary. The relation between treatment efficacy, as measured by PFS-1, and biomarkers will be assessed with proportional hazards models in terms of treatment, the biomarker, the biomarker by treatment interaction, age, sex, race, and baseline tumor K-RAS status (mutated, wild type). Significant effects will be described and illustrated, as appropriate, with Kaplan Meier plots by strata determined by biomarker level and treatment group, for example.

Sample size justification: Historically, the mPFS for previously treated mCRC patients treated with RGF is 1.9 mos. We predict VOR/HCQ will improve mPFS to 3.8 months. We expect 5% lost to follow-up. Assuming a 36-month accrual period with 1 year for follow up, 36 subjects per group are necessary to obtain 80% power. With 5% lost to follow-up the sample size required per group is 38 ($=36/0.95$), therefore, the total required sample size is 76 subjects. As a result, the target accrual rate is 3-4 patients/month to achieve a target accrual at 36 months with an additional 12-month follow-up.

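### Section 10 drops randomised patients who leave before finishing Cycle 1 from the PFS-1 comparison, and no all-randomised PFS-1 analysis is planned

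*Combined protocol and SAP*

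**What the plan says.** Section 10.0, in the analytic plan for the primary objective, gives the adjusted proportional hazards model for PFS-1 and then states: "If a patient does not complete Cycle 1 and is off study, then this patient will not be evaluable for efficacy". Such a patient stays evaluable for toxicity. The interim rule follows, including the provision that "a statistical basis for stopping the study for futility will be attained if the conditional power is less than or equal to 20" per cent.

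PFS-1 runs from the start of the first assigned treatment "until the date the criteria for progression are met or the date the patient is taken off study for any reason", whichever comes first (Section 5.7; the Synopsis and Section 7.0 agree).

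Analysis sets are named for only two time-to-event endpoints. For OS: "The analyses of median OS will be performed in the intent-to-treat population". For PFS-2 it is the crossover population. None is named for PFS-1. The biomarker plan in Section 10 treats PFS-1 as the efficacy measure: "The relation between treatment efficacy, as measured by PFS-1, and biomarkers will be assessed with proportional hazards models".

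On crossover, the Synopsis says: "If crossover is not done, then the patient will be off study and can go on to receive other treatments". Crossover is optional and left to the physician.

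**The concern.** Membership of the efficacy set depends on what happens to a patient after randomisation, so the comparison is no longer between the groups that were randomised. A treated patient who is taken off study in week 3 has a PFS-1 time of under four weeks, and the rule discards it. The patients most likely to be discarded are those who did worst.

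The word efficacy carries the rule beyond the final PFS-1 test to response, the interim efficacy and futility tests, and the PFS-1 biomarker models. It also leaves OS unreconciled, because OS is an efficacy endpoint assigned to intent-to-treat.

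Being off study is partly discretionary. A patient who fails early and is offered crossover is arguably still on study; the same patient without crossover is off study and dropped. The text does not say what happens to a patient who crosses over and leaves soon after.

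Because no other PFS-1 analysis is planned, the plan contains nothing that would show the effect of the exclusion.

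**Working it through.** **Inputs from the documents.** Medians 1.9 (RGF) and 3.8 months (VOR/HCQ), 36 per group for 80% power, 38 after 5% loss, 36 months of accrual plus 12 of follow-up, final critical value 1.96857 (Section 10); 4-week cycles (Section 5.0); first on-treatment CT after 2 cycles (Section 5.3.1). **Assumed.** Exponential PFS, two-sided alpha 0.05 (the plan does not state it), and all Cycle 1 exit rates.

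**1. The plan's sample size reproduces.** Freedman events = (1.960 + 0.842)² × [(1 + 0.5)/(1 − 0.5)]² = 7.85 × 9 ≈ 71. With mean event probability 0.991, 71/(2 × 0.991) = 35.8, so 36 per arm. 36/0.95 = 37.9, so 38 per arm and 76 in total. The allowance is 2 patients per arm, labelled loss to follow-up; nothing is allowed for Cycle 1 exclusions.

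**2. How many patients could be affected.** 28 days = 28/30.4375 = 0.920 months.
- RGF: 1 − 2^(−0.920/1.9) = 28.5%, or 10.8 of 38.
- VOR/HCQ: 1 − 2^(−0.920/3.8) = 15.4%, or 5.9 of 38.

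These are upper guides, because progression seen only on the scan after Cycle 2 is not a Cycle 1 exit.

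**3. All failures within 28 days dropped.** Unadjusted log-rank simulation, 38 per arm, 5% random loss, critical value 1.96857, no interim look, at least 20,000 runs per scenario.

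| Scenario | All analysed | Rule applied |
|---|---|---|
| Planned medians: power | about 80% | about 69% |
| Equal medians: false positives, each direction | 2.5–2.7% | 2.7–3.0% |
| Planned medians, 15% extra Cycle 1 failures on VOR/HCQ only: chance of declaring benefit | about 50% | about 66% |

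Without the 5% loss, the first row is 83% against 73% and the third 52% against 69%, with estimated hazard ratios in the third of 0.65 against 0.54. With equal medians and the same 15% extra failure on VOR/HCQ, the hazard ratio is 1.15 with everyone and 1.01 under the rule. The excess disappears from view. If the extra 15% falls on RGF instead (planned medians, no loss), the chance of declaring benefit is 92% with everyone and 69% under the rule, so the distortion can run either way.

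**4. Milder exclusion.** Power from 38 per arm = Φ(√[76 × (1 − e) × 0.991]/3 − 1.960), where e is the share excluded regardless of outcome: 82.5% at e = 0, 80.5% at 5%, 78.4% at 10%, 76.0% at 15%, 73.5% at 20%. Section 2.4.1 reports 31 enrolled in phase I of the combination and 27 evaluable for dose-limiting toxicity, three having deteriorated rapidly in cycle 1. Borrowing 3/31 = 9.7% and 4/31 = 12.9% gives about 77–79%. Those patients had mixed tumours and 21-day cycles, so the rates are only a rough guide.

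**5. Unequal removal under the null.** Here only some of each arm's Cycle 1 failures are removed.
- 5% or 10% from both arms: about 2.7% false VOR/HCQ superiority, no bias.
- 5% of RGF and 10% of VOR/HCQ: about 4%.
- 5% of RGF and 20% of VOR/HCQ: about 9%.
- 20% of RGF and 5% of VOR/HCQ: about 9% false VOR/HCQ inferiority.

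**The case against.** **An endpoint definition and an analysis set are different things.** A reader might infer that the rule contradicts the PFS-1 definition. It does not, strictly: a patient can have a PFS-1 time and still be outside the evaluable set. What stands is the mismatch, with no second analysis to cover it. The rule's absence from the Synopsis adds little, since the Synopsis omits the PFS-1 model too.

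**The false-positive figures need differential removal.** A reader might infer that the rule inflates the type I error to about 9%. The documents do not support that. If every Cycle 1 failure leaves the study and is dropped, step 3 shows essentially no inflation. The 4% and 9% figures require some early failures to be kept and others dropped at different rates by arm, through exit practice or the crossover decision. With the first scan after Cycle 2, crossovers for progression in Cycle 1 should be few. This is a secondary risk.

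**The direction is unknown.** A reader might infer that the rule favours VOR/HCQ. The plan cites 54% grade 3 or more events with RGF (Section 2.2.1) and no grade 4 or 5 events in its earlier VOR/HCQ studies (Synopsis). The grades differ and neither figure is a Cycle 1 exit rate, so they do not settle which arm would lose more patients.

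**Including everyone is not enough by itself.** This objection stands. Section 5.7 does not say whether going off study without progression or death is an event or is censored. With about 5% of RGF and 20% of VOR/HCQ patients leaving for reasons unrelated to progression, power at the planned medians is 43% if these exits are events, 75% if censored and 72% if excluded. If 5% and 20% exits are really failures, censoring them gives 10.7% false VOR/HCQ superiority under the null. The repair must therefore settle this rule too.

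**Conclusion.** The concern holds as a defect in the primary analysis set. Followed as written, the plan drops randomised patients from the PFS-1 comparison on a post-randomisation outcome, and it has no analysis that would reveal the effect. This rests on the text; the simulations only size it.

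The main harm is concealed early failure and lower power: at most about 80% to 69% at the planned medians, or about 77–79% at the borrowed phase I rates. With 15% extra early failure on VOR/HCQ, the chance of declaring benefit is 66% where analysing everyone gives 50%. False-positive inflation to about 4% or 9% is possible only under assumed differential removal. All exit rates are assumptions, and exponential PFS is assumed throughout.

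It should be corrected before analysis, because it governs the primary test and, through the word efficacy, the interim decision.

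**What to change.** Replace the sentence in Section 10 with: *PFS-1 is analysed in all randomised patients in the arm assigned, including those who leave before completing Cycle 1; all treated patients are evaluable for toxicity.*

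In the same edit:
- State that progression and death are PFS-1 events. State whether going off study without either is an event or is censored, and run the other choice as a labelled sensitivity analysis.
- State how randomised patients who never start treatment are handled, since the PFS-1 clock starts at first treatment.
- Use the same set for response and for the interim efficacy and futility tests, and confirm that OS stays intent-to-treat.
- Keep the Cycle 1 completer set as a sensitivity analysis only.
- Report Cycle 1 exits by arm and reason.

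**Cost.** A paragraph in Section 10, an event and censoring rule wherever PFS-1 is defined (Synopsis, Sections 5.7 and 7.0), and two sensitivity analyses. No extra patients: 38 per arm already gives about 80% power with everyone analysed. Observed medians may look slightly less favourable than under the exclusion. For example, removing 5% as early failures lifts a true 1.9-month median to 1.9 × log₂[1/(0.5 × 0.95)] = 2.04 months, and the change gives up that gain.
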